4. OBJECTIVES

PRIMARY

Determine the progression-free survival (PFS) of ramucirumab in advanced biliary cancers (intrahepatic cholangiocarcinoma, extrahepatic cholangiocarcinoma, and gallbladder cancer) who have received prior chemotherapy.

SECONDARY

- Determine the response rate (RR) and disease control rate (partial response + complete response + stable disease) of ramucirumab in advanced biliary cancers
- Determine overall survival (OS) of ramucirumab in advanced biliary cancers
- Evaluate the toxicity of ramucirumab in advanced biliary cancers

EXPLORATORY

- Correlate the carbohydrate antigen (CA) 19-9 response (defined as >50% decrease from baseline) with tumor response, PFS and OS
- Correlate baseline tumor gene expression profile with PFS
- Correlate pre- and post-therapy CT imaging to quantify iodine content, atomic numbers, and Z-values and correlate with response

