6. TREATMENT PLAN

This is an open-label phase II study. Patients with advanced biliary cancers will be enrolled. All patients must be registered on the M. D. Anderson Cancer Center Clinical Oncology Research (CORE) system prior to initiation of treatment.

This study will enroll up to 60 patients to at MD Anderson Cancer Center. Accrual is projected to be 2.5 subjects per month. If this study proceeds to a future trial for patients with DNA repair gene of FGFR mutations, data obtained from this expanded cohort of 10 patients will be included in final analysis.

This will be an open-label, single arm study with each cycle being 14 days. Ramucirumab will be administered at 8 mg/kg intravenously on day 1 of the cycle. Restaging will be done every 4 cycles (+/- 1week). Treatment will be continued until progression unless other reasons for study discontinuation occur as listed in section 8 “Criteria for Removal from the Study.” Additionally, patients who have therapy interrupted for consolidative therapies (including, but not limited to radiation therapy, radioembolization, and chemoembolization) or at the physician’s discretion, will remain on study for survival analyses.

Table 2: Starting Dose Level

Drug	Dose	Infusion Time	Schedule (in 14-day cycle)
IV Ramucirumab	8 mg/kg	60 min (+/- 5 min)	Day 1

Dosing and Administration

The study drug will be provided by the sponsor and administered in the following order with the specified pre-medications:

- Premedication should be with an IV H₁ agonist, diphenhydramine 50 mg in NS 50 mL IV within 30 minutes prior to treatment
- Ramucirumab 8 mg/kg in NS to final volume of 250 mL IV over 60 minute on day 1 repeated every 14 days

Dose Modifications and Toxicity Management

Dose modifications and treatment delays based on observed drug-related toxicity will be performed as described below. Any toxicity associated or possibly associated with ramucirumab treatment should be managed according to standard medical practice.

Specific adverse events of concern, which may or may not be associated with ramucirumab therapy, include infusion reactions, hypertension, arterial or venous thrombotic events, bleeding (hemorrhagic) events, and proteinuria. These are specified in greater detail below.

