7. EVALUATION DURING STUDY

- Patients must begin Cycle 1 within 14 days of signing the informed consent document and after the screening assessments. Treatment will be administered by qualified and trained site personnel in a hospital, clinic, or other out-patient setting appropriate for chemotherapeutic infusions. All assessments should be performed within 72 hours of each specified time parameter, with the exception of Cycle 1 in which assessments must be conducted within 24 hours (except those noted), or if medical or scheduling conditions require a delay. Request of 20 unstained tumor slides of 5 to 10 microns thick will be sent at enrollment.

Day 1 of each cycle (except where noted)

- Inclusion/exclusion review (Cycle 1 only)
- Directed physical exam
- Vital Signs
- Measurement of weight (kg) and BSA calculation prior to dosing.
- ECOG Performance Status (see Appendix 1)
- Hematology: CBC with differential and platelet count

- Serum chemistries: glucose, creatinine, BUN, total bilirubin, AST, ALT, alkaline phosphatase albumin, LDH, total protein, and electrolytes (sodium, potassium, phosphorus, chloride, CO₂, magnesium, calcium). In patients with known Gilbert’s syndrome, it is recommended to perform a direct bilirubin and indirect bilirubin.
- CA 19-9
- Urinalysis
- AEs using the NCI CTCAE (<http://ctep.info.nih.gov>)
- Concomitant medication notation

Prior to Cycles 4, 8, 12, etc.

- In order to more precisely determine time to progression, the investigator is encouraged to obtain radiological assessments earlier if there is a strong clinical suspicion of disease progression, in order to either confirm or refute the clinical impression.
- Reassessment of the extent of tumor should be made by the same imaging methods used to establish baseline tumor measurements.

Table 7: Study Assessments (treatment cycle is 14 days)

Evaluation or Procedure	Screening ¹	Study Treatment	End of Treatment Evaluation ¹¹	30-day Post-Treatment Evaluation ¹² /Long Term Follow-up
		On or before Day 1 of each cycle		
Informed consent	X			
Medical History	X			
Physical Examination	X	X ^{3,4}	X	
Inclusion/Exclusion criteria	X			
Height	X			
Weight	X	X ^{3,4}	X	
Vital Signs (Blood Pressure)	X	X ^{3,4}	X	
ECOG Performance Status	X	X ^{3,4}	X	
Hematology ¹⁰	X	X ^{3,4}	X	
Biochemistry ¹⁰	X	X ^{3,4}	X	
Urinalysis ¹⁰	X	X ^{3,4}	X	
Serum or urine pregnancy test (for females of child-bearing potential)	X			
Tumor Tissue Collection	X ²			
Toxicity assessment	X	X ^{3,4}	X	X ⁸

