10. Hematology: complete blood count with differential. Chemistry: glucose, creatinine, BUN, total bilirubin, AST, ALT, alkaline phosphatase, albumin, LDH, total protein, and electrolytes (sodium, potassium, phosphorus, chloride, C02, magnesium, calcium). Tumor markers (CA19-9) as indicated. Tumor markers are performed every 2 cycles. In patients with known Gilbert's syndrome, it is recommended to perform a direct bilirubin and indirect bilirubin.
11. Within 10 days of decision to discontinue study treatment.
12. At 28-45 days from last dose of study medication.

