7.1 End of treatment evaluations

Within 10 days of decision to discontinue treatment

- The investigator will evaluate the results of the following clinical and laboratory assessments to be conducted at the time the patient discontinues study treatment:
- Physical examination with neuropathy assessment
- ECOG Performance Status
- Weight
- Vital signs (blood pressure)
- Hematology: complete blood count with differential
- Biochemistry: glucose, creatinine, BUN, total bilirubin, AST, ALT, alkaline phosphatase albumin, LDH, total protein, and electrolytes (sodium, potassium, phosphorus, chloride, CO₂, magnesium, calcium). Tumor markers (CA19-9) as indicated. In patients with known Gilbert's syndrome, it is recommended to perform a direct bilirubin and indirect bilirubin.
- Urinalysis
- Concomitant medication notation
- Toxicity (adverse events) assessment (including neurologic toxicities) using NCT CTCAE Version 4.0
- Tumor evaluations including CT scan or MRI of the chest, abdomen, and pelvis (if recent imaging within 4 weeks, tumor evaluation does not need to be repeated)

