9.7 Guidelines for evaluation of measurable disease

All measurements should be taken and recorded in metric notation using a ruler or calipers. All baseline evaluations should be performed as closely as possible to the beginning of treatment and never more than 4 weeks before the beginning of the treatment.

The same method of assessment and the same technique should be used to characterize each identified and reported lesion at baseline and during follow-up. Imaging-based evaluation is preferred to evaluation by clinical examination when both methods have been used to assess the antitumor effect of a treatment.

Clinical lesions. Clinical lesions will only be considered measurable when they are superficial (e.g., skin nodules and palpable lymph nodes). In the case of skin lesions, documentation by color photography, including a ruler to estimate the size of the lesion, is recommended.

Chest x-ray. Lesions on chest x-ray are acceptable as measurable lesions when they are clearly defined and surrounded by aerated lung. However, CT is preferable.

Conventional CT and Magnetic Resonance Imaging. Conventional CT and MRI should be performed to obtain images of 5 mm or less slice thickness.

Tumor markers. Tumor markers alone cannot be used to assess response. If markers are initially above the upper normal limit, they must normalize for a patient to be considered in complete clinical response.

Cytology, Histology. These techniques can be used to differentiate between partial responses (PR) and complete responses (CR) in rare cases (e.g., residual lesions in tumor types, such as germ cell tumors, where known residual benign tumors can remain). The cytological confirmation of the neoplastic origin of any effusion that appears or worsens during treatment when the measurable tumor has met criteria for response or stable disease is mandatory to differentiate between response or stable disease (an effusion may be a side effect of the treatment) and progressive disease.

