10.6 Analysis method

Data analysis will be performed using SAS or S-plus, as appropriate. The median PFS time will be estimated by Bayesian posterior estimates, along with the 95% credible interval. Toxicity will be reported by type, frequency and severity. Highest toxicity grades per patient per course will be tabulated for adverse events and laboratory measurements.

Demographic and baseline laboratory results will be summarized using descriptive statistics, including means with standard deviations, or medians with ranges, histograms and box-plot. Fisher's exact test and Wilcoxon rank test will be used in the data analyses of categorical and continuous variables, respectively. Progression-free survival and overall survival functions will be estimated using the Kaplan-Meier method. The two-sided log-rank test will be used to assess the differences of time to events between groups, and Cox proportional hazards model will also be fitted to evaluate the association between time-to-event outcomes and tumor gene expressions. The correlation between pre- and post- therapy CT imaging results will be assessed through Spearman correlation and Wilcoxon signed rank test will be used to assess whether the change in CT imaging between pre- and post-therapy is statistically significant. In addition, logistic regression analyses will be performed to assess the association between CT imaging results or CA19-9 response (defined as >50% decrease from baseline) and tumor response.

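### The CA 19-9 schedule is inconsistent, and the CA 19-9 response definition has no raised-baseline requirement, time point or confirmation rule, so the exploratory responder variable is poorly defined

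*Combined protocol and SAP*

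**What the plan says.** Four places set the timing of CA 19-9.

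- Section 7 places it in the list headed "Day 1 of each cycle (except where noted". No exception stands beside it, whereas the eligibility review in the same list is marked as Cycle 1 only.
- Table 7 has no CA 19-9 row. The marker enters through footnote 10, attached to the hematology, biochemistry and urinalysis rows: "Tumor markers (CA19-9) as indicated. Tumor markers are performed every 2 cycles".
- Section 7.1 (end of treatment) says "Tumor markers (CA19-9) as indicated".
- Section 6 sets the time scale, "each cycle being 14 days", with restaging every 4 cycles.

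Two places define how the marker is used. The exploratory objective in section 4 is to "Correlate the carbohydrate antigen (CA) 19-9 response (defined as >50% decrease from baseline) with tumor response, PFS and OS". Section 10.6 plans logistic regression for the association between "CA19-9 response (defined as >50% decrease from baseline) and tumor response". Neither states a minimum baseline, a time point, a confirmation rule or an evaluable set.

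Section 9.7, by contrast, conditions its own marker rule on the baseline value: "If markers are initially above the upper normal limit, they must normalize for a patient to be considered in complete clinical response". Section 9.8 repeats that condition.

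**The concern.** There are two separate problems.

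**Who is classified.** A percentage fall is informative about the tumour only if the marker was raised to begin with. Sections 9.7 and 9.8 show that the authors foresaw markers that are not raised at baseline, but the response definition has no matching condition. As written, a patient with a normal baseline is either a non-responder or, after a change inside the normal range, a responder. Neither label says anything about drug effect, and mixing such patients in weakens the association that the objective sets out to estimate.

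**On how many values.** The text supports more than one draw frequency and does not say which value decides the classification. If one qualifying value is enough, each further draw is another chance to qualify. Patients drawn more often, or treated for longer, are then more likely to be called responders. The second dependence matters most for PFS and OS, because staying on treatment helps to create the responder status that is then compared with outcome.

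**Working it through.** The plan states no CA 19-9 response rate, variability, sample size or power, so there is no figure to reproduce. The steps below count draws from the plan's own schedule and then size the effects under stated assumptions.

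**1. Number of post-baseline draws** (14-day cycles, section 6)

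| Up to | Every cycle | Every 2 cycles |
|---|---|---|
| Week 8 (56 days, first restaging) | 56/14 = 4 | 2 |
| 2.73 months (83 days, median PFS of the initial cohort, section 2) | 5 | 2 or 3 |
| 3.0 months (91 days, expected median PFS, section 10.2) | 6 | 3 |

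The entry of 2 or 3 arises because footnote 10 does not say which cycle starts the count.

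**2. Schedule effect by week 8, if any single fall counts.** Assumptions: log CA 19-9 changes linearly in each patient; weekly slopes have mean +0.03 and SD 0.06 or 0.10; each value, including baseline, carries log-scale noise with SD 0.15, 0.25 or 0.35; 400,000 simulated patients. A responder has any value below half of baseline. Draws are at weeks 2, 4, 6, 8 or at weeks 4, 8.

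| Slope SD | Noise SD | Every cycle | Every 2 cycles | Gap (points) |
|---|---|---|---|---|
| 0.06 | 0.15 | 4.3% | 3.8% | 0.5 |
| 0.06 | 0.25 | 10.0% | 7.3% | 2.7 |
| 0.06 | 0.35 | 19.0% | 12.7% | 6.3 |
| 0.10 | 0.15 | 13.7% | 13.0% | 0.7 |
| 0.10 | 0.25 | 18.2% | 15.6% | 2.6 |
| 0.10 | 0.35 | 25.2% | 19.5% | 5.7 |

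The gap runs from about 0.5 to 6 points and depends mainly on noise. A second model gave a similar range. It continued draws to progression, with exponential PFS (median 2.73 to 3.0 months), log slope of mean +0.1 and SD 0.3 per 28 days, and noise SD 0.2 to 0.4. The shares were 15.5 to 29.2% against 13.7 to 21.9%, a gap of about 2 to 7 points.

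**3. Effect of time on treatment, with the schedule held fixed.** In the first model with draws every 4 weeks, the share with any qualifying fall is about 4 to 20% after 8 weeks of draws and about 17 to 35% after 24 weeks. Within each setting the difference is about 13 to 16 points. Part of this is continuing true decline rather than repeated chances. Section 2 reports 6 patients treated beyond 24 weeks, so the range of treatment durations is real.

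**4. Normal baselines.** Let r be the response rate among raised-baseline patients and q the share starting normal, and suppose that none of the latter qualifies. The overall rate is r × (1 − q). With r = 1/3 assumed:

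- q = 0.20 (12 of 60 patients): 1/3 × 0.80 = 27%
- q = 0.40 (24 of 60 patients): 1/3 × 0.60 = 20%

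If some normal-baseline patients qualify by fluctuation, the overall rate falls less, but those responders are spurious.

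**The case against.** The strongest reply is that the plan never says that any one fall is enough. Sections 4 and 10.6 are silent on time point and confirmation. If response were read at one fixed visit common to both numeric schedules, the draw-count effect would vanish. That is correct, and it is why steps 2 and 3 are conditional. The defect the documents do show is that the deciding value is undefined.

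Second, the schedule can be partly harmonised. The exception clause in the section 7 heading may point to footnote 10, and that footnote may mean every 2 cycles on treatment and as indicated otherwise. This is a possible reading, but the text does not state it, and the CA 19-9 item carries no note. A reader might go further and infer that some patients need have no on-treatment value, or no baseline. The documents do not support that. The sentence after the as-indicated wording calls for draws every 2 cycles, the laboratory rows carry a Screening mark, and the Day 1 list includes Cycle 1. A baseline is arguably planned; it should be stated as required.

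Third, the sizes rest wholly on assumed inputs. At the low-noise end the schedule gap is under 1 point, and 6 points of 60 patients is 0.06 × 60 = 3.6 patients. This stands. The simulations also compare whole-cohort schedules and do not model draw frequency that differs between patients.

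Fourth, a reader might infer harm to complete-response assessment, since section 9.8 requires a raised marker to normalise. With a 0% response rate in the initial cohort (section 2), that consequence is minor.

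**Conclusion.** The point holds as a defect of definition in an exploratory analysis. The schedule statements need reconciling, and the cut-off applies to normal-baseline patients because nothing excludes them. The second part does not depend on how often the marker is drawn.

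The size cannot be derived from the documents. Under the assumptions shown, the schedule gap is about 0.5 to 6 points by week 8, and only if any single fall counts. Under that same reading, unequal time on treatment matters more than the schedule, at about 13 to 16 points between 8 and 24 weeks of draws. If 20 to 40% start normal, a 33% response rate among raised-baseline patients reads as 20 to 27% overall.

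Two stronger conclusions should be resisted. The result does not bear on the primary PFS estimate, the futility rule or the toxicity rule, none of which uses CA 19-9. Nor do the documents say that some patients fail to produce the marker; they support only the distinction between raised and normal baselines.

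**What to change.** **Schedule.** Reconcile section 7, Table 7 footnote 10 and section 7.1 to one CA 19-9 schedule. State the cycle from which any 2-cycle count starts, require a baseline value, give the marker its own row in Table 7, and delete the as-indicated wording for on-treatment draws. A common set of visits should not be assumed for patients already enrolled until the starting cycle is known: if markers were drawn at even cycles, a grid of Cycles 3, 5 and 7 would discard every 2-cycle value.

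**Definition.** In sections 4 and 10.6, restrict the CA 19-9 response analysis to patients with a baseline above the upper limit of normal, and report the others separately. Score response in one fixed window, for example scheduled draws up to the first restaging after 4 cycles, and say whether a fall must be confirmed. Relate response to PFS and OS from the end of that window among patients still at risk then, so that longer treatment cannot create responders. A common schedule without a fixed window would leave that dependence in place.

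**Cost.** These are wording changes, and blood is already drawn on Day 1. The price is numbers. With 20 to 40% of 60 patients starting normal, 36 to 48 remain. Assuming exponential PFS with median 2.73 to 3.0 months, the share event-free at 56 days (1.84 months) is 0.5^(1.84/2.73) = 0.63 to 0.5^(1.84/3.0) = 0.65. That leaves roughly 23 to 31 patients for the PFS comparison; the OS comparison loses only patients who have died or been lost to follow-up by then. Draws off the schedule or after the window would not be used for classification.

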7.1 End of treatment evaluations

Within 10 days of decision to discontinue treatment

- The investigator will evaluate the results of the following clinical and laboratory assessments to be conducted at the time the patient discontinues study treatment:
- Physical examination with neuropathy assessment
- ECOG Performance Status
- Weight
- Vital signs (blood pressure)
- Hematology: complete blood count with differential
- Biochemistry: glucose, creatinine, BUN, total bilirubin, AST, ALT, alkaline phosphatase albumin, LDH, total protein, and electrolytes (sodium, potassium, phosphorus, chloride, CO₂, magnesium, calcium). Tumor markers (CA19-9) as indicated. In patients with known Gilbert's syndrome, it is recommended to perform a direct bilirubin and indirect bilirubin.
- Urinalysis
- Concomitant medication notation
- Toxicity (adverse events) assessment (including neurologic toxicities) using NCT CTCAE Version 4.0
- Tumor evaluations including CT scan or MRI of the chest, abdomen, and pelvis (if recent imaging within 4 weeks, tumor evaluation does not need to be repeated)

7.2 Follow-up (off-treatment)

Follow-up/observation for all treatment related adverse events will be through Day 30 (Day 28 to Day 45 allowed) following the last dose of study drug or until resolution or stabilization of the toxicity or start of another treatment regimen. If it is not feasible for the patient to return to M. D. Anderson for the Day 30 toxicity assessment, the patient will be contacted by phone for this assessment.

Patients with documented (radiological) disease progression at any point during the study will discontinue treatment with study drugs under this protocol. Objective evidence of progressive disease will be recorded at the time of progression. Patients without evidence of progression while on study, regardless of the number of treatment cycles received, will be followed for progression until it is documented. If a patient is off treatment with no documented disease progression and no subsequent anti-cancer treatment is received, he/she should be followed every 12 weeks (+/- 5 weeks) after the End of Treatment Evaluation visit with tumor evaluations until disease progression is documented or for 12 months after their first dose of study drug, whichever comes first.

7.3 Long-term followup

All patients will be followed for survival status approximately every 3 months 30-day post-treatment evaluation. Survival status may be obtained by checking the electronic medical record or by telephone call.

8. CRITERIA FOR REMOVAL FROM THE STUDY

Subjects who meet the following criteria should be discontinued from study treatment:

- Disease progression
- Intercurrent illness that prevents further administration of treatment
- Unacceptable adverse event(s) as determined by the treating physician
- Patient decides to withdraw from the study
- General or specific changes in the patient's condition render the patient unacceptable for further treatment in the judgment of the investigator.

9. RESPONSE EVALUATION

9.1 Measurement of effect

Response and progression will be evaluated in this study using the new international RECIST criteria (version 1.1, 2009) proposed by the RECIST committee³³. All patients who have measurable disease according to the RECIST criteria and who have their disease re-evaluated will be evaluable for response. For the purposes of this study, patients should be reevaluated for response approximately every 4 cycles. Note: Lesions are either measurable or non-measurable using the criteria provided below. The term "evaluable" in reference to measurability will not be used because it does not provide additional meaning or accuracy.

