9.9 Time point evaluation

At each protocol specified time point, a response assessment occurs. Table 9 provides a summary of this for patients who have measurable disease at baseline. Table 10 provides a summary of this for patients with non-measurable (therefore non-target) disease.

Table 8: Response for measurable disease

Target Lesions	Non-target Lesions	New Lesions	Overall Response	Best Response for this Category also Requires
CR	CR	No	CR	≥ 4 weeks Confirmation
CR	Non-CR/Non-PD	No	PR	≥ 4 weeks Confirmation
CR	Not evaluated	No	PR	
PR	Non-PD or not all evaluated	No	PR	
SD	Non-PD or not all evaluated	No	SD	Documented at least once ≥ 6 weeks from baseline
Not All Evaluated	Non-PD	No	NE	NE
PD	Any	Yes or No	PD	No prior SD, PR or CR
Any	PD*	Yes or No	PD	
Any	Any	Yes	PD	

* In exceptional circumstances, unequivocal progression in non-target lesions may be accepted as disease progression. NE = inevaluable Note: Patients with a global deterioration of health status requiring discontinuation of treatment without objective evidence of disease progression at that time should be reported as “symptomatic deterioration.” Every effort should be made to document the objective progression even after discontinuation of treatment.

Table 9: Response for non-measurable disease

Non-target Lesions	New Lesions	Overall Response
CR	No	CR
Non-CR/Non-PD	No	Non-CR/Non-PD
Not all evaluated	No	NE
Unequivocal PD	Yes or No	PD
Any	Yes	PD

NE = inevaluable a 'Non-CR/non-PD' is preferred over 'stable disease' for non-target disease since SD is increasingly used as endpoint for assessment of efficacy in some trials so to assign this category when no lesions can be measured is not advised.

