9.10 Evaluation of best overall response

The best overall response is the best response recorded from the start of the treatment until disease progression/recurrence (taking as reference for progressive disease the smallest measurements recorded since the treatment started). The patient's best response assignment will depend on the achievement of both measurement and confirmation criteria.

Table 10: Response Assignment

Overall Response First Time Point	Overall Response Subsequent Time Point	BEST Overall Response
CR	CR	CR
CR	PR	SD, PD, or PR
CR	SD	SD provided minimum criteria for SD duration met, otherwise, PD
CR	PD	SD provided minimum criteria for SD duration met, otherwise, PD
CR	NE	SD provided minimum criteria for SD duration met, otherwise, NE
PR	CR	PR
PR	PR	PR
PR	SD	SD
PR	PD	SD provided minimum criteria for SD duration met, otherwise, PD
PR	NE	SD provided minimum criteria for SD duration met, otherwise, NE
NE	NE	NE

NE = inevaluable. If a CR is *truly* met at first time point, then any disease seen at a subsequent time point, even disease meeting PR criteria relative to baseline, makes the disease PD at that point (since disease must have reappeared after CR). Best response would depend on whether minimum duration for SD was met. However, sometimes ‘CR’ may be claimed when subsequent scans suggest small lesions were likely still present and in fact, the patient had PR, not CR at the first time point. Under these circumstances, the original CR should be changed to PR and the best response is PR.

Patients with a global deterioration of health status requiring discontinuation of treatment without objective evidence of disease progression at that time should be classified as having “symptomatic deterioration.” Every effort should be made to document the objective progression, even after discontinuation of treatment.

In some circumstances, it may be difficult to distinguish residual disease from normal tissue. When the evaluation of complete response depends on this determination, it is recommended that the residual lesion be investigated (fine needle aspirate/biopsy) before confirming the complete response status.

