9.11 Confirmation

To be assigned a status of PR or CR, changes in tumor measurements must be confirmed by repeat assessment at a minimum follow-up interval of 6 weeks after the criteria for response are first met. In the case of SD, follow-up measurements must have met the SD criteria at least once after study entry at a minimum interval of 6 weeks.

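### No denominator is stated for response rate or disease control rate; the evaluability rule in section 9.1, if used as one, can raise the disease control rate but never lower it

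*Combined protocol and SAP*

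**What the plan says.** Section 4 lists as a secondary objective the response rate together with the "disease control rate (partial response + complete response + stable disease"). It names no analysis set.

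Section 9.1 holds the only population rule for response: "All patients who have measurable disease according to the RECIST criteria and who have their disease re-evaluated will be evaluable for response". Two conditions must be met: measurable disease and a re-evaluation.

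Stable disease needs a later measurement. Section 9.11 states that "follow-up measurements must have met the SD criteria at least once after study entry at a minimum interval of 6 weeks", and Table 8 asks for the same. CR and PR must be confirmed at a second assessment (9.8, 9.11). Tables 8 to 10 contain an NE category, but nothing says whether NE patients stay in a denominator.

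Section 10.6 gives estimation methods for PFS and OS and tabulation for toxicity. It uses tumor response as the outcome of a logistic regression, but gives no analysis set, estimator or interval for response rate or DCR. Sections 10.1 to 10.5 give none either.

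Section 2 reports for the first cohort 43 enrolled, 42 treated, a response rate of 0% and a DCR of 44%. Median PFS is tied there to the treated patients; the DCR has no stated base.

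**The concern.** An analyst who needs a denominator finds only section 9.1. Used that way, the rule removes patients for a reason related to outcome: those who die, deteriorate or withdraw before a first post-baseline scan. None of them can be in the numerator, so the error has one direction.

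What is at stake is the credibility of a secondary endpoint. With no responders in the first cohort, DCR is the only response-based result that can differ from zero, and readers may set it beside rates from other second-line studies. No test, threshold or decision rule depends on it.

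**Working it through.** **Inputs.** From section 2: 43 enrolled, 42 treated, DCR 44%, median OS 6.31 months with lower 95% limit 4.7 months. From section 6: 14-day cycles and "Restaging will be done every 4 cycles (+/- 1week"), which puts the first scan at 4 × 14 = 56 days, weeks 7 to 9. Section 7 instead speaks of imaging before cycle 4, which is 3 × 14 = 42 days, week 6. Not in the documents: the number x never re-evaluated, the number with measurable disease, and the count behind the 44%.

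**1. Can the 44% be reproduced?** Not on the 42 treated: 18/42 = 42.9% and 19/42 = 45.2%. By ordinary rounding it fits 19/43 (44.2%), 18/41 (43.9%), 17/39 (43.6%), 16/36 (44.4%) and 15/34 (44.1%). The base cannot be recovered.

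**2. Direction.** Let c be the number with CR, PR or SD, and N the treated patients with measurable disease. The rate over all N is c/N; under 9.1 it is c/(N − x). The x patients contribute nothing to c, because each of the three categories needs a post-baseline assessment. The ratio of the two rates is N/(N − x), which is at least 1.

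**3. Size for assumed x.** N = 42 assumes that every treated patient had measurable disease. The last column assumes c = 18, the count over 42 nearest to 44%.

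| x | 42/(42 − x) | 18/(42 − x) |
|---|---|---|
| 0 | 1.00 | 42.9% |
| 1 | 1.02 | 43.9% |
| 2 | 1.05 | 45.0% |
| 4 | 1.11 | 47.4% |
| 6 | 1.17 | 50.0% |
| 8 | 1.24 | 52.9% |

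Eligibility does not require measurable disease. If only 36 had it (assumption), the factor is 36/35 = 1.03 for x = 1, 36/33 = 1.09 for x = 3 and 36/30 = 1.20 for x = 6. The exact 95% interval for 18/42 is 27.7% to 59.0%, so all the shifts shown lie within sampling error. Unlike sampling error, they go one way only.

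**4. Is x likely to be zero?** As a rough scale, take a constant death hazard, so that the share dead by time t is 1 − exp(−ln 2 × t/m), where m is the median OS. Week 6 is 42/30.4375 = 1.380 months and week 8 is 56/30.4375 = 1.840 months.

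- m = 6.31: 14.1% by week 6 and 18.3% by week 8, or 5.9 and 7.7 of 42.
- m = 4.7: 18.4% and 23.8%, or 7.7 and 10.0 of 42.

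These figures neither estimate nor bound x. Some of these patients would have had an earlier scan, and ECOG 0–1 patients may die later than a constant hazard implies. In the other direction, withdrawal, intercurrent illness and toxicity (section 8) can also end treatment before a scan.

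**The case against.** The strongest reply is that no harm is shown. Section 9.1 says who is evaluable; it never calls that group a denominator, and section 10 does not refer to it. The one reported DCR fits all enrolled patients. On that base, the rate over the 42 treated would be 19/42 = 45.2%, slightly higher than reported. This stands: the documents do not show that anyone was left out.

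The protocol also works to keep x small. It encourages earlier scans when progression is suspected (section 7), asks for end-of-treatment and follow-up imaging (7.1, 7.2), allows clinical measurement of some lesions ("Clinical lesions will only be considered measurable when they are superficial", 9.7), and says of symptomatic deterioration that "Every effort should be made to document the objective progression even after discontinuation of treatment" (9.9, repeated in 9.10). This stands in part. None of it reaches a patient who dies before any scan. The end-of-treatment scan may also be skipped if imaging exists within 4 weeks, and after a very early stop the baseline scan could satisfy that.

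Little depends on the endpoint. Deaths count as PFS events (10.2), so early failures appear there and in OS. This stands, and it limits the weight of the point.

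Finally, printing n/N might seem enough, and the choice between all treated patients and all treated patients with measurable disease is partly preference. The documents do not choose, and either is defensible if stated. But n/N alone does not settle how NE and unassessed patients are counted.

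**Conclusion.** The point holds as a gap with a one-directional consequence. No denominator is stated, and the only available rule, if used as one, raises the DCR by N/(N − x) or leaves it unchanged. For an assumed x of 0 to 8 of 42 the factor is 1.00 to 1.24. The response rate stays at 0% on any base while there are no responders. PFS, futility monitoring, toxicity monitoring and sample size are not touched.

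Two stronger readings are tempting. A reader might infer that the reported 44% is inflated; it fits 19/43 as well as smaller bases, so this does not follow. A reader might also take the 6 to 8 early deaths implied by the 6.31-month median as the most that could be lost. That figure counts deaths only and uses a point estimate; the lower confidence limit gives about 8 to 10, and other early exits could add to it. The documents give x no upper bound, and x may also be zero.

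**What to change.** In sections 9.1 and 10.6:

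- Make all treated patients with measurable disease at baseline the main denominator for response rate and DCR.
- Count patients with no post-baseline assessment, or with best response NE, as not responding and not controlled.
- Report the re-evaluated subset as supplementary.
- Describe patients without measurable disease separately, using the Table 9 categories.
- Give numerator and denominator for every rate, including the 44% in section 2.
- State that the definition was set after the first cohort's results were known.

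The cost is wording only, with no new visits or data. The DCR may come out slightly lower, and the definition is post hoc for the 42 patients already treated. This is a cheap improvement to a secondary endpoint.
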